11.0 Privacy/Confidentiality Issues

A database will be designed for this study using REDCap (Research Electronic Data Capture) tools. REDCap is a secure, web-based application designed to support data capture for research studies, providing validated data entry, audit trails, seamless data downloads to common statistical packages, and mechanisms for importing data from external sources. It will reside on a secure server with access provided exclusively to the research personnel. Subjects will be identified with a study identification number. A key to the subject identification number will be kept in a separate locked file drawer to which only the Principal Investigator and research coordinators have access. Reports will thereby be generated without Protected Health Information (PHI) data, and access will be restricted so that statisticians, etc. don't have access to all data.

Risk of leakage of PHI is minimized by keeping paper records in a locked cabinet and maintaining computerized records in the password protected REDCap data base. The principal investigator and the research staff are trained in HIPAA privacy regulations. The participant's identification is concealed, and a number is used as the identifier instead of the subject's name. Only the principal investigator or members of the research team will have the list of study patient's names as the correlate with the study number.

12.0 Follow-up and Record Retention

The study is anticipated to last for up to four years. The study results will be maintained indefinitely for research purposes.

APPENDIX 1: Overnight Insulin Infusion Prior to STUDY 1-3 visits (T1DM Participants only)

Overnight Insulin Infusion Protocol

The following insulin infusion protocol is intended for use in T1DM participants in the setting of the overnight insulin infusion prior to hyperinsulinemic clamp studies. Target blood glucose is **90-119 mg/dL**.

Initiating the Insulin Infusion

1. START TIME: the overnight infusion should begin once IV access is obtained the evening before the clamp study unless directed otherwise.
2. TWO PHASES OF INSULIN INFUSION: The IV insulin infusion will proceed in two phases. First, we will infuse insulin at a constant rate from the time IV access is obtained after admission through midnight. This insulin infusion rate will equal the basal infusion rate provided by the participants' insulin pumps at home. Second, beginning at midnight and continuing through the clamp study in the morning, we will adjust the insulin infusion rate each hour as needed to reach a constant blood glucose concentration of 90-119 mg/dL.
3. PREPARATION FOR INFUSION: insulin will be dispensed as 100 units diluted in 100 mL of 0.9% NaCl.
 - a. PRIMING: flush 10 mL of insulin infusion through all IV tubing before insulin infusion begins (to saturate insulin binding sites in the tubing).
 - b. CARRIER FLUID: 0.9% NaCl fluid at 20 mL/hr can be run with the IV insulin infusion to keep the vein open.
 - c. HYPOGLYCEMIA PREVENTION: 20% dextrose solution should be hung and ready in case of hypoglycemia. Glucagon should be within easy reach.
4. TRANSITIONING FROM HOME INSULIN REGIMEN: T1DM participants will use an insulin pump at home. When IV access is obtained and you are ready to begin the IV insulin infusion, ask the participant to suspend and disconnect his or her insulin pump immediately before starting the overnight insulin infusion
5. INITIAL IV INSULIN INFUSION RATE: initial infusion rate will equal the basal rate being infused by the participant at home using their insulin pump.

Example: Home insulin pump basal rate = Humalog 0.8 units/hr
 Initial IV insulin infusion rate = 0.8 unit/hr

Blood glucose (BG) Monitoring

1. Check BG hourly on the hour beginning at 2300 and record BG and insulin infusion rate on the task flowsheet on the designated line.

Changing the Insulin Infusion Rate (Beginning at Midnight)

Beginning with the Midnight BG and with each subsequent BG check, change the insulin infusion rate as follows:

IF BG < 55 mg/dL:

STOP INSULIN INFUSION

- Bolus 100 mL of D20 (20 gm of glucose) immediately
- Contact PI ([name], mobile: [REDACTED] pager [REDACTED])
- Check BG q 15 minutes
- When BG is ≥ 90 mg/dL, wait 1 hour, recheck BG. If still ≥ 90 mg/dL, restart insulin infusion at 50% of the most recent rate

IF BG 55-69 mg/dL:

STOP INSULIN INFUSION

- Contact PI immediately ([name], mobile: [REDACTED] pager [REDACTED])
- Prepare to give D20 at approximately 3.0 mg/kg/min after discussing with PI.
- Check BG q 15 minutes
- When BG is ≥ 90 mg/dL, wait 1 hour, recheck BG. If still ≥ 90 mg/dL, restart insulin infusion at 75% of the most recent rate

IF BG > 70 mg/dL:

STEP 1: Determine the CURRENT BG LEVEL. This identifies a COLUMN in the table:

BG 70-89 mg/dL	BG 90-119 mg/dL	BG 120-179 mg/dL	BG \geq 180 mg/dL
----------------	-----------------	------------------	---------------------

STEP 2: Determine the RATE OF CHANGE from the prior BG level. This identifies a CELL in the table. Then move to the right for **INSTRUCTIONS**. (Note: if the last BG was measured less than an hour before the current BG, calculate the hourly rate of change. Example: if the BG at 0200 was 85 mg/dL and an additional BG is checked early at 0230 was 70 mg/dL, the total change over 30 minutes is -15 mg/dL; however, the hourly rate of change is $-15 \text{ mg/dL} \times 2 = -30 \text{ mg/dL}$).

BG 70-89 mg/dL	BG 90-119 mg/dL	BG 120-179 mg/dL	BG \geq 180 mg/dL	INSTRUCTIONS*
		BG \uparrow by > 40 mg/dL/hr	BG \uparrow	\uparrow INFUSION by “ 2Δ ”
	BG \uparrow by > 20 mg/dL/hr	BG \uparrow by 1-40 mg/dL/hr OR BG UNCHANGED	BG UNCHANGED OR BG \downarrow by 1-40 mg/dL/hr	\uparrow INFUSION by “ Δ ”
BG \uparrow	BG \uparrow by 1-20 mg/dL/hr, BG UNCHANGED, OR BG \downarrow by 1-20 mg/dL/hr	BG \downarrow by 1-40 mg/dL/hr	BG \downarrow by 41-80 mg/dL/hr	NO INFUSION CHANGE
BG unchanged OR BG \downarrow by 1-20 mg/dL/hr	BG \downarrow by 21-40 mg/dL/hr	BG \downarrow by 41-80 mg/dL/hr	BG \downarrow by 81-120 mg/dL/hr	\downarrow INFUSION by “ Δ ”
BG \downarrow by > 20 mg/dL/hr see below†	BG \downarrow by > 40 mg/dL/hr	BG \downarrow by > 80 mg/dL/hr	BG \downarrow by > 120 mg/dL/hr	HOLD x 30 min, then \downarrow INFUSION by “ 2Δ ”

Protocol Version #:6

Protocol Date: July 29, 2021

53

***CHANGES IN INSULIN INFUSION RATE** (“ Δ ”) are determined by the current rate:

Current Rate (units/hr)	Δ = Rate Change (units/hr)	2Δ = 2X Rate Change (units/hr)
≤ 1	0.25	0.5
>1-3	0.5	1
> 3	1	2

† **DISCONTINUE** insulin infusion. Check BG q 30 min; when BG is ≥ 90 mg/dL restart insulin infusion at 75% of most recent rate

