6.1.3.1 Arrival and Preparation

Preparation: To ensure an accurate measurement of key study outcomes with minimal confounding, participants will take the following precautions before each STUDY visit:

- Hold vitamin supplementation for 72 hours
- Avoid NSAIDs and aspirin for 24 and 72 hours, respectively, if feasible

- Refrain from smoking and avoid secondhand smoke exposure for 12 hours
- Consume no caffeine for 12 hours
- Abstain from exercise for 12 hours

Study participants will arrive to the CRC between 1700-2100 on the evening prior to STUDY visits.

[figure not shown]
CRC staff will draw the following labs prior to conducting the clamp study:

- Pregnancy test (urine or blood) on female participants to rule out pregnancy.
- I-STAT potassium: to screen for hypokalemia

T1DM participants who use an insulin pump will discontinue and detach their insulin pump at 2130 on the night of CRC admission. T1DM participants who take multiple daily insulin injections take their last basal insulin analog dose on the evening prior CRC admission and hold their basal insulin dose on the evening of admission. CRC staff or KSP will place an intravenous angiocatheters in each arm.

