6.1.3.2 Overnight insulin infusion (T1DM SUBSTUDY participants only)

At 2200 a continuous, IV infusion of regular human insulin (recombinant DNA origin) will be given to T1DM participants according to the protocol of Goldberg et al.(59), modified for use in healthy patients with T1DM (Appendix 1). This protocol targets a glucose of 90-120 mg/dL by the next morning. CRC staff will check blood glucose of T1DM participants on an hourly basis using a calibrated, hospital bedside glucose monitor. This protocol was implemented in a previous study (IRB # 161504) and achieved ideal glycemic control as shown in the figure below (n=9 T1DM participants, figure shows means \pm SD for glucose and means for insulin infusion rate).

Should glucose fall to < 75 mg/dL, the PI may elect to infuse a small dose of 20% dextrose to prevent hypoglycemia. Should glucose fall to < 55 mg/dL and the patient experiences symptoms of hypoglycemia, 20% dextrose will be at bedside to treat the hypoglycemia (e.g. 75 mL of 20% dextrose delivers 15 gm of glucose). If glucose were to fall to < 55 mg/dL, the PI will postpone the following morning's clamp study to a later date because of the confounding influence of the counter-regulatory response to hypoglycemia.

The PI will be readily available to CRC nursing staff via telephone and [REDACTED]

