7.1.1 Glucose monitoring

Glucose levels will be monitored every hour during the overnight insulin infusion for T1DM participants as outlined in Appendix 1. Because CONTROL SUBSTUDY participants will receive IV insulin overnight prior to STUDY 5 and 7, we will monitor every hour in the CRC on the night preceding these studies. We will monitor plasma glucose concentrations every 5-10 minutes throughout the hyperinsulinemic clamp to guide the variable dextrose infusion and ensure euglycemia. Because of the frequent glucose monitoring, the study team can quickly detect a trend toward hypoglycemia before it actually occurs. If hypoglycemia does occur, however, this frequent monitoring allows for rapid detection of the low glucose concentration and rapid corrective treatment with an infusion of IV glucose (dextrose).

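### Appendix 1 and the protocol body contradict each other on when the overnight insulin infusion starts, when the pump comes off, when glucose checks begin and when the low-glucose stop instructions apply

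*Combined protocol and SAP*

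**What the plan says.** The instructions are spread over four places.

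- **Section 6.1.3.1** has participants arrive between 1700 and 2100 and says "T1DM participants who use an insulin pump will discontinue and detach their insulin pump at 2130 on the night of CRC admission". It then mentions catheter placement, without a clock time.
- **Section 6.1.3.2** begins "At 2200 a continuous, IV infusion of regular human insulin", refers to Appendix 1 for the method, and requires hourly bedside glucose. It allows dextrose at the investigator's election below 75 mg/dL, and has dextrose at the bedside for symptomatic glucose below 55 mg/dL. Glucose below 55 mg/dL postpones the clamp.
- **Section 7.1.1** lists monitoring as a safeguard: "Glucose levels will be monitored every hour during the overnight insulin infusion for T1DM participants as outlined in Appendix 1".
- **Appendix 1**, item 1, reads "START TIME: the overnight infusion should begin once IV access is obtained the evening before the clamp study unless directed otherwise". Item 2 adds "First, we will infuse insulin at a constant rate from the time IV access is obtained after admission through midnight". Item 4 disconnects the pump immediately before the infusion starts. The monitoring instruction is "Check BG hourly on the hour beginning at 2300 and record BG and insulin infusion rate". The part on changing the infusion rate opens "Beginning with the Midnight BG and with each subsequent BG check, change the insulin infusion rate as follows". Under that lead-in come the two instructions to stop insulin, for glucose below 55 and for 55-69 mg/dL, followed by the titration table.

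**The concern.** These are bedside safety instructions for an insulin infusion, and staff cannot follow all of them at once. Section 6.1.3.2 delegates the infusion to Appendix 1, and Appendix 1 is written to the person running it, so it is likely to be the working document. Section 7.1.1 cites it as the source of the hourly monitoring. Section 7.5.2 in turn relies on section 7.1 when it argues that the risk to adolescents is only a minor increase over minimal risk. If Appendix 1 does not deliver what section 7.1.1 attributes to it, that argument is weaker than it reads.

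There is also a lesser, scientific side. Section 6.1 describes the three STUDY 1-3 visits as identical. If the start time is open, the length of fixed-rate insulin before titration can differ between visits of the same participant, and a glucose below 55 mg/dL costs the visit. The documents give no figure from which the effect on the morning steady state or on lost visits could be estimated, so none is claimed here.

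**Working it through.** The plan states no figure to reproduce. The check sets the clock times side by side and takes differences.

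| Item | Body | Appendix 1 |
|---|---|---|
| Infusion start | 2200 (6.1.3.2) | at IV access, unless directed otherwise (item 1); at IV access (item 2) |
| Pump off | 2130 (6.1.3.1) | immediately before the infusion (item 4) |
| Glucose checks | hourly during the infusion (6.1.3.2, 7.1.1) | hourly from 2300 |
| Instruction to stop insulin | none | below 55 and 55-69 mg/dL, from the midnight reading |

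**Pump to infusion, following the body for both.** 2200 − 2130 = 30 min with neither pump nor intravenous insulin. Appendix 1 has no such interval.

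**Time on insulin before the first Appendix 1 check and before its first stop instruction.**

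- Time to first check = 2300 − start.
- Time to first stop instruction = 2400 − start.

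The time of IV access is not stated. Assumption: access comes 30 min after arrival, so a 1700-2100 arrival gives a start between 1730 and 2130.

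| Start | Basis | To first check | To first stop instruction |
|---|---|---|---|
| 2200 | section 6.1.3.2 | 1 h | 2 h |
| 2130 | latest arrival + 30 min | 1.5 h | 2.5 h |
| 1730 | earliest arrival + 30 min | 5.5 h | 6.5 h |

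**What needs no assumption about access.** In the 2200 row the first check is exactly one hour in, so monitoring is hourly and the check conflict disappears. The stop-instruction gap does not: the 2300 reading falls inside the 2 h before the midnight lead-in takes effect, while item 2 keeps the rate constant. A 2300 value below 70 mg/dL therefore has no Appendix 1 action attached. The dextrose text in section 6.1.3.2 is not tied to midnight, but it does not say to stop insulin.

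**What depends on access.** Any start before 2200 makes the first Appendix 1 check later than one hour, contrary to section 7.1.1. Arrival from 1700 makes such a start possible. It does not show that it will happen.

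**The case against.** The strongest reply is that the documents can be read together. Item 1 of Appendix 1 yields to other direction, and section 6.1.3.2 gives 2200 in the same sentence that invokes the appendix. A first check at 2300 fits a 2200 start exactly. In section 6.1.3.1 the catheters are mentioned after the 2130 pump detachment, which would suit access near 2130-2200. That would mean 1 to 1.5 h to the first check, not 5.5 h.

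There is also cover before midnight. A licensed clinician is on call overnight (section 7.1.2), and Appendix 1 has dextrose hung and glucagon within reach. Before midnight the infusion runs at the home basal rate and replaces the pump. After midnight it is titrated hourly. Section 6.1.3.2 reports good glucose control in nine earlier participants, and a lost visit can be rescheduled (section 6.1.3.13).

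Much of this stands. A reader might infer that the protocol leaves hours of insulin with no glucose check at all. The documents do not support that: sections 6.1.3.2 and 7.1.1 require hourly checks throughout the infusion, so the longer gaps describe Appendix 1 followed alone.

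The reply does not dispose of the rest:

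- Item 2 repeats the IV-access start without the qualifier, and nothing in Appendix 1 names 2200.
- A 2200 start leaves the midnight lead-in as it is.
- On-call cover lets someone decide to stop insulin, but it is not a written instruction to do so.
- The home basal rate is defined from a pump, whereas section 6.1.3.1 also provides for participants on injections.
- The report on nine participants does not say which start time or check schedule was used.
- Figure 6 is not available here. Whatever it shows, it would not remove the conflicting text.

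**Conclusion.** The contradiction is real and should be resolved before staff rely on these instructions. Start time and pump-off time differ outright in wording. The hourly monitoring that section 7.1.1 attributes to Appendix 1 holds only for a start at 2200 or later. The firmest element is the 2 h, on the body's own start time, in which Appendix 1 attaches no action to a low reading and the body gives no instruction to stop insulin. The 30 min without pump or intravenous insulin also follows directly from the stated times.

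The ranges of 1.5-5.5 h and 2.5-6.5 h rest on two conditions: Appendix 1 is followed without the body, and access comes 30 min after arrival. Their upper ends need the earliest arrival and are worst cases, not expected values. The existing cover lowers the risk but does not make the passages agree.

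**What to change.** Reconcile sections 6.1.3.1, 6.1.3.2 and 7.1.1 with Appendix 1 in one amendment, so that a single consistent statement, applying to all STUDY 1-3 visits, covers:

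1. when the infusion starts;
2. when the pump is disconnected;
3. when the first glucose check is made;
4. when the low-glucose actions, including the instructions to stop insulin, take effect.

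The medical lead decides which times and rules are correct; no choice among them is proposed here. The cost is amendment wording and, depending on what is decided, perhaps a few more bedside glucose checks before 2300. Sample size and analysis are unaffected.
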